6.5.1 Rescue Medications

Protocol specific analgesic rescue medication for endometriosis-associated pain will include four equivalent NSAID choices and three equivalent opioid choices. The protocol-allowed analgesic rescue medications for endometriosis-associated pain are presented in Table 6–3. Investigators will prescribe a specific analgesic rescue medication for subjects at the time of Visit 2, taking into consideration the subject's preference and/or historical use of analgesics and the investigator's clinical judgement (based on the approved options).

Investigators are not to suggest or advise subjects on any modifications to their rescue medication regimen. Subjects will be instructed to contact the site if a change in their rescue analgesic medication is needed, such that appropriate adjustments can be considered. Investigators may then prescribe a different analgesic rescue medication (from each medication class if necessary) for the subject. Investigators should not prescribe more than one analgesic rescue medication from the same medication class at one time. The dosage outlined in Table 6-3 could be utilized, but all prescribed use of rescue analgesic medication should be according to appropriate clinical practice standards and the investigator's clinical judgment.

It is the investigator's discretion whether to withdraw a subject due to an analgesic issue.

Prophylactic use of protocol-specific rescue analgesic medications is not allowed. Use of any other analgesic medications for endometriosis-associated pain, including prophylactically, is not allowed from Visit 2 through the Follow-up Period.

Daily use of rescue analgesic medications taken for endometriosis-associated pain will be recorded by the subject in the e-Diary from Visit 2 through the Follow-up period including date of rescue medication use as well as the name, dosage and total number of the rescue medication within a 24-hour period. Detailed information on the rescue medication that will be sourced and provided to the subject can be found in the site operation manual. In addition, any pain medication taken for pain other than for rescue (such as treatment for toothache etc.) will be recorded in eCRF, not in the e-Diary.

Use of a prohibited medication for treatment of endometriosis-associated pain will be documented in the eCRF. If a subject continues to take analgesic(s) other than the protocol-

Version 6.0 42 of 138 April 11, 2024

specified rescue analgesics for endometriosis-associated pain, her continued participation in the study will be evaluated by the investigator and the Medical Monitor.

If there are any questions regarding rescue therapy, please contact your Medical Monitor.

Table 6-3. Permitted Rescue Medication for Endometriosis-Associated Pain

Medication class	Medication Name	Dosing Strength*	Country
NSAIDS	Ibuprofen	200 mg	All
NSAIDS	Naproxen [#]	200 mg	All
NSAIDS	Diclofenac [^]	25 mg	All
NSAIDS	Celecoxib	50 mg	All
Opioid Analgesics	Hydrocodone	5 mg Hydrocodone+	All
	+acetaminophen	300 or 325 mg acetaminophen	
Opioid Analgesics	Codeine phosphate	30 mg codeine+300 mg	All
	+acetaminophen\$	acetaminophen\$	
Opioid Analgesics	Tramadol	37.5mg tramadol	All
, F3	+ acetaminophen	+ 325mg acetaminophen	

^{*} Use of these rescue analgesic medications should be according to appropriate clinical practice standards and Investigator's clinical judgment.

6.5.2 Prohibited Medications

The following medications are prohibited for the entire study duration.

Table 6-4. Prohibited Medications

Prohibited Medications
Hormonal/Anti-Hormonal Therapy
GnRH agonist
GnRH antagonists
Danazol
Medroxyprogesterone Acetate
Contraceptives (e.g. oral, patch, injectable and implanted)
Levonorgestrel (except emergency contraception, i.e., levonorgestrel 1.5 mg)
Other Progestins (e.g. oral, injectable, patch, vaginal, IUDs, implanted)
Mifepristone
Testosterone preparations

Version 6.0 43 of 138 April 11, 2024

[#] Naproxen 200 mg is equivalent to naproxen sodium 220 mg.

[^] Diclofenac Immediate-Release product is preferred.

^{\$} Combination with or without caffeine is permitted.

Prohibited Medications		
Aromatase Inhibitors		
Menotropins and human ch	norionic gonadotropin (hCG)	
	Medications that affect PRL level	
Antiepileptics and anticonvulsants	Diazepam, Phenytoin Sodium, Phenobarbital, etc.	
Antipsychotics and antidepressants	Sulpiride, Risperidone, Haloperidol, Clomipramine, Phenothiazines, Nomifensine, etc.	
Injection use of Histamine H1/H2 receptor antagonists	Promethazine, Famotidine. etc.	
Other medications that affect PRL level	Bromocriptine, Cabergoline, Lergotrile, Lisuride, Metergoline, Quinagolide, Terguride, Isoniazide, Domperidone, Metoclopramide, Reserpine, Methyldopa, etc.	

Analgesics

Any analgesic medications other than protocol specified ones for endometriosis-associated pain, including prophylactically

Osteoporosis drugs

Bisphosphonates, Denosumab, Teriparatide, Abaloparatide, Romosozumab and Calcitonin.

Strontium or Fluoride (other than for dental indication).

Selective estrogen receptor modulators: Raloxifene, Bazedoxifene, Lasofoxifene, etc.; Clomifene, Tamoxifen, etc.

Others

Growth hormone replacement

Cannabinoids

Systemic corticosteroids (oral or injectable)

Misoprostol

Herbal remedies containing Hypericum perforatum (e.g. Kava kava and St. John's wort)

Anti-tumor necrosis factor (TNF)/anti-nerve growth factor (NGF)

Medications that are covered by **urine drug screen** (if applicable)

If in the Investigator's opinion, subject needs to take prohibited medication(s) continuously for any reason, her continued participation in the study will be evaluated by the investigator and the Medical Monitor.

If a hormonal emergency contraception is used, the use of the drug and any associated menstrual cycle irregularity after the use should be documented.

If there are medications not listed in the table above that need further clarification, consult the Hope Medicine Medical Monitor for suggestions.

6.6 Dose Modification

Not applicable.

6.7 Intervention After the End of the Study

There will be no study intervention after the end of the study. Subjects could follow the routine medical practice.

7 Discontinuation of IMP and Subject Withdrawal

7.1 Discontinuation of IMP

It may be necessary for a subject to permanently discontinue (definitive discontinuation) the IMP. If the IMP is definitively discontinued, the subject will remain in the study until Visit 10 to be evaluated for safety and efficacy of the IMP. Please refer to Section 10.4 and 8.4.5 for details on contraceptive guidance and collection of pregnancy information.

The Investigator or Medical Monitor (and, if needed, with DMC review) may temporarily hold or stop the dosing of IMP to a subject at any time during the study. For subjects that discontinue IMP for reasons related to safety, unblinding of the treatment assigned to the subject may be carried out if deemed necessary by the Sponsor to assess any potential safety signal or by the Investigator to provide adequate medical care to the subject. All details of reasons, therapies that may have been subsequently started should be well documented and reviewed.

Examples of conditions or symptoms that may warrant holding or stopping IMP at the Investigator's and/or Medical Monitor's discretion include:

- Occurrence of a severe or serious AE assessed as related to IMP
- Repeating premature ventricular contractions (PVC) confirmed by additional ECG examination at least 30 minutes apart, or QTcF interval >500 ms, or increase in QTcF interval >60 ms compared to baseline in absence of possible causes other than the IMP
- Significant decrease of neutrophils count < 1500 mm³ confirmed by repeat measurement

Version 6.0 45 of 138 April 11, 2024

- Pregnancy
- Intolerance of the IMP authorized under this protocol
- If in the Investigator's opinion, continuation with the administration of the IMP would be detrimental to the subject's well-being

Investigator must notify the Sponsor within one calendar day of being aware of an event that may warrant holding or stopping the IMP. If the IMP is held due to safety concerns, approval by the Medical Monitor is required prior to resumption of IMP. If the subject meets the holding or stopping conditions again after resumption (re-challenge), the IMP will be permanently discontinued.

Unless informed consent is withdrawn, subjects who permanently discontinue IMP during the treatment period should attend all subsequent visits up to Visit 10 and complete all procedures (except IMP administration related) as outlined in the SoA.

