2.3.1 Risk Assessment

Table 2-1. Risk Assessment

Potential Risk of Clinical	Summary of Data/Rationale for Risk	Mitigation Strategy
Significance	KISK	
	HMI-115	
Non-clinical Risks Pituitary gland function (endocrinology)	Nonclinical - toxicology studies in monkeys demonstrated HMI-115 to elevate PRL levels which may influence other hormone levels. In the 26-week toxicity study in male and female cynomolgus monkeys treated with 24 and 100	In the FiH study, the hormone TSH, cortisol, somatotropin, FSH, LH, and estradiol were evaluated and no significant changes observed in the doses tested. The hormonal levels will be monitored in this study as higher doses of HMI-115 will be
	mg/kg of HMI-115 weekly, no HMI-115 related changes were noted in hormone detection (testosterone, estradiol and progesterone) throughout the study.	administered. The impact of treatment with HMI-115 on other hormones remains to be investigated further
Non-Clinical Risk Mammary gland function	Toxicology studies in Cynomolgus monkeys showed a minimal reversible atrophy of the mammary gland	Changes in mammary gland function is reversed after a dosing- free period. Treatment contraindicated during pregnancy and lactation and in women with abnormal clinical findings during mammography

Potential Risk of Clinical	Summary of Data/Rationale for	Mitigation Strategy
Significance	Risk	
Clinical Risk	Neutropenia was reported in one	Careful monitoring of subjects for
Immune function	subject in the Phase 1 study (subject	any ongoing, subclinical infection
	already had a neutrophil count that	and exclusion of patients with
	was lower than the lower limit of	existing immunosuppression.
	normal [LLN] prior to enrollment)	
Non-Clinical Risk	Slight increase in single ectopic	Monitoring of electrocardiographic
Cardiovascular system	ventricular heart beats in	parameters through ECG
	Cynomolgus monkey at highest	measurements.
	tested dose (At the No Observed	
	Adverse Effect Level (NOAEL) in	
	the cardiovascular safety study	
	there is an 11-fold safety margin for	
	the 240 mg Q2W dose based on	
	C_{max}).	
Clinical Risk	Increased PRL may cause disorder	Collect galactorrhea, change in
PRLR blockade may induce PRL	in the secretion of other sex	menstrual cycles with oligo- or
over secretion. Whether it affects	hormones and dopamine and further	amenorrhea, Hirsutism, Acne,
secretion of other sex hormones and	induce conditions such as	change in mood, etc., as adverse

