7.2 Subject Withdrawal from the Study

The subject may withdraw or may be withdrawn from the study:

- If they decide to do so, at any time and irrespective of the reason
- At the specific request of the Sponsor

Subject discontinuation from IMP or withdrawal from the study should be avoided as much as possible. Every attempt should be made to restart IMP if medically appropriate and approved by Medical Monitor, irrespective of the duration of holding IMP.

In the event of withdrawn from the study during the treatment period, if possible, an early discontinuation visit (procedures same as Visit 9) needs to be performed as soon as possible and an on-site follow-up visit (procedures same as Visit 10) after 12 weeks from the last dose should be conducted. If the subject is unwilling to attend the on-site follow-up visit, a follow-up phone call should be attempted if the subject agrees, to collect safety information (monitoring AE, pregnancy status, concomitant medications) (refer to Section 1.3).

In the event of withdrawn from the study during the follow-up period, if possible, an on-site follow-up visit (procedures same as Visit 10) is recommended to complete as soon as possible followed by a phone call follow-up at 12 weeks from the last dose to collect safety information (monitoring AE, pregnancy status, concomitant medications). If the subject is unwilling to attend an on-site

Version 6.0 46 of 138 April 11, 2024

follow-up visit, a phone call follow-up at 12 weeks from the last dose should be attempted if the subject agrees (refer to Section 1.3).

If the subject withdraws informed consent for disclosure of future information, the Sponsor may retain and continue to use any data collected before such a withdrawal of consent.

Note: For subjects discontinued from IMP or withdrawn from study, no additional PK and ADA sampling except EOT and EOS visits (if possible) is required after IMP discontinuation.

Handling of subjects with suspected COVID-19 infection:

If a subject develops fever or symptoms suspected of being a result of COVID-19 during the study, they will be instructed to follow-up with their regular healthcare provider or follow the instructions for suspected COVID-19 cases per their local health authority.

A subject may be withdrawn by the Investigator based on discussion with the Sponsor and Medical Monitor under the following circumstance:

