8.4.5 Pregnancy

All subjects should follow contraceptive guidance strictly as detailed in Section 10.4. However, in the event of pregnancy after start of study visit with relevant consent obtained:

- Details of all pregnancies in subjects will be collected from the signing of ICF until the end of study participation.
- If a pregnancy is reported, the Investigator should inform the Sponsor (or Sponsor designated agent) within 24 hours of learning of the pregnancy and complete the pregnancy report forms within 30 days.
- Investigator will collect pregnancy information on any subject, who becomes pregnant while participating in this study. Subject will be followed to determine the outcome of the pregnancy. The Investigator will collect follow-up information on the subject and neonate for one month after delivery, which will be forwarded to the Sponsor. For live infant births, information on the health of the infant will be collected 6 to 12 months after delivery.
- Any termination of pregnancy will be reported, regardless of fetal status (presence or absence of anomalies) or indication for procedure.
- IMP should be discontinued permanently when pregnancy is identified.

Version 6.0 57 of 138 April 11, 2024

Pregnancy alone is not regarded as an AE. Abnormal pregnancy outcomes (e.g., spontaneous abortion, fetal death, stillbirth, congenital anomalies, ectopic pregnancy) are considered to be SAEs.

Elective abortions without complications should not be handled as AEs, unless the abortion was required for treatment of a specific AE. Hospitalization for normal delivery of a healthy newborn should not be considered a SAE.

Any SAE that occurs during pregnancy (including SAEs occurring after last administration of IMP) must be recorded on the SAE report form (e.g., maternal serious complications, spontaneous or therapeutic abortion, ectopic pregnancy, stillbirth, neonatal death, congenital anomaly, or birth defect) and reported within 24 hours in accordance with the procedure for reporting SAEs.

Any SAE occurring as a result of a post-study pregnancy which is considered reasonably related to the IMP by the Investigator, will be reported to the Sponsor. While the Investigator is not obligated to actively seek this information in former study subjects, he or she may learn of an SAE through spontaneous reporting.

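### Protocol 7.1 leaves pregnancy to a discretionary hold or stop of IMP, while 8.4.5 calls for permanent discontinuation; the two sections need one rule

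*Protocol*

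**What the plan says.** Four places in the protocol bear on IMP and pregnancy.

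- **Section 7.1 (Discontinuation of IMP)** introduces a list of examples as "conditions or symptoms that may warrant holding or stopping IMP at the" discretion of the Investigator and/or Medical Monitor. Pregnancy is one bullet, without qualification. Two general sentences follow the list: "If the IMP is held due to safety concerns, approval by the Medical Monitor is required prior to resumption of IMP", and "If the subject meets the holding or stopping conditions again after resumption (re-challenge), the IMP will be permanently discontinued". Neither mentions pregnancy.
- **Section 7.2 (Subject Withdrawal from the Study)** asks sites to avoid discontinuation where they can and adds: "Every attempt should be made to restart IMP if medically appropriate and approved by Medical Monitor, irrespective of the duration of holding IMP".
- **Section 8.4.5 (Pregnancy)** says: "IMP should be discontinued permanently when pregnancy is identified". It mentions no hold, no discretion and no resumption.
- **Table 2-1 (Risk Assessment)**, in the row on mammary gland function, gives as mitigation: "Treatment contraindicated during pregnancy and lactation".

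The opening paragraph of 7.1 sends the reader to 10.4 and 8.4.5, but only for contraception advice and the gathering of pregnancy data. The SAP gives no rule on stopping IMP for pregnancy.

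**The concern.** Site staff who have to decide about the next dose will look in section 7, which carries discontinuation in its title. There, pregnancy has the same standing as an ECG finding or a low neutrophil count: something that may justify a hold or a stop, at discretion. The instruction to discontinue permanently is one bullet in a section otherwise about collecting and reporting pregnancy information.

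Two sites could therefore handle the same positive test differently, each with a protocol section to point to. The stake is consistent conduct in a matter of fetal exposure, in a trial whose section 10.4 regards all subjects as of childbearing potential (those with documented bilateral salpingectomy or tubal ligation are excepted from the contraception requirements).

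**Working it through.** No arithmetic on alpha, power or sample size applies. The check sets the passages side by side, then asks when the difference could matter.

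**Step 1. Compare the two rules.**

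| Question | Protocol 7.1 | Protocol 8.4.5 |
|---|---|---|
| Is action left to discretion? | Yes, Investigator and/or Medical Monitor | None stated |
| Is a temporary hold open? | Yes, hold or stop | Not provided for |
| Is resumption possible? | After a safety hold, with Medical Monitor approval; pregnancy not excepted | Not provided for |
| When is discontinuation required to be permanent? | When a condition is met again after re-challenge | When pregnancy is identified |

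**Step 2. Can a site follow both?** Yes. Section 7.1 allows a hold or a stop; 8.4.5 allows only a permanent stop. A permanent stop lies within both. What 7.1 allows and 8.4.5 does not is a hold that leaves resumption open.

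**Step 3. Does the cross-reference settle it?** No. It leads to 8.4.5 for other purposes and does not say that 8.4.5 governs dosing. A reader who follows it will come across the rule; a reader who has no need of contraception or reporting detail will not.

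**Step 4. Do 7.2 and Table 2-1 conflict as well?** The restart sentence in 7.2 is conditional on medical appropriateness and Medical Monitor approval, so it does not by itself contradict 8.4.5. It simply does not except pregnancy. Table 2-1 agrees with 8.4.5. The mismatch is between 7.1 and 8.4.5.

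**Step 5. When would it matter?** The Schedule of Activities gives six doses, at Visits 3 to 8, and urine tests at Visits 3, 5, 7, 9 and 10. IMP is given after the visit's tests.

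- Visit 3: a negative result is required before randomization, so no dosing decision under 7.1 arises.
- Visit 5: two doses have been given (Visits 3 and 4), so 6 − 2 = 4 remain.
- Visit 7: four doses have been given (Visits 3 to 6), so 6 − 4 = 2 remain.
- Visits 9 and 10: all six doses are already past.

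Two of the five scheduled urine tests can therefore lead to a hold-or-stop decision. A pregnancy found between visits while doses remain would raise the same question.

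**Step 6. Is there an effect on the primary analysis?** SAP 7.2.1 defines the intercurrent event as premature withdrawal from study treatment for any reason, and SAP 7.2.2 sets values after it to missing and re-imputes them. Neither section says how a hold that is never lifted is classed. The Week 12 score needs a cycle with at least two days of menstruation, so in an ongoing pregnancy it may be missing and be imputed in any case. Depending on timing, the closest-menstruation rule might instead pick an earlier cycle. Nothing here shows a change in the estimate.

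**The case against.** The best reply is that this is a general list beside a specific rule. The 7.1 list gives examples, it includes stopping, and nobody who stops IMP permanently breaches it. Section 8.4.5 is devoted to pregnancy, and a reader would normally let the specific section prevail. Resumption after pregnancy is only inferred: the sentence concerns holds for safety concerns, while 8.4.5 says that pregnancy on its own does not count as an adverse event. The conditions in 7.2, read with Table 2-1, make re-dosing in pregnancy unlikely. All of this stands, and it limits the weight of the point. It does not make the two texts agree, because nothing in 7.1 says that pregnancy is outside the discretion or that 8.4.5 takes precedence.

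Two stronger readings are tempting and are not supported.

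- A reader might infer that the protocol directs sites to restart IMP in a pregnant subject. It does not: no sentence in 7.1 or 7.2 names pregnancy in connection with resumption, and the restart sentence carries two conditions.
- A reader might infer that a subject put on hold would escape the hypothetical-strategy step of the primary analysis. No passage says so. The intercurrent event covers withdrawal for any reason, and the SAP is silent on whether an unresumed hold counts as withdrawal. Silence does not establish exclusion.

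There is also a version limit. The SAP's introduction rests on Protocol 6.1 (19 September 2024), whereas the protocol available here is 6.0 (11 April 2024). Whether the wording survived cannot be checked.

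**Conclusion.** The inconsistency is real and narrow. Section 7.1 read alone permits a temporary hold for pregnancy; 8.4.5 does not. The issue is wording that affects patient safety and uniform site conduct, with no demonstrated consequence for the estimand, the imputation or the power.

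Its practical reach is a pregnancy found before the last dose at Visit 8, which among scheduled tests means Visits 5 and 7. The number of such cases cannot be estimated, because the documents give no rate.

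The conclusion assumes that the 7.1 resumption sentences apply to every condition in the list, since none is excepted, and that Protocol 6.0 reflects the wording in force. It takes no position on which clinical rule is right.

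**What to change.** First check whether Protocol 6.1 already resolves the point. If it does not:

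- Reconcile 7.1 with 8.4.5 so that one rule for IMP in pregnancy applies throughout the protocol.
- Check the restart sentence in 7.2 and the statement in Table 2-1 against that rule.
- Add a cross-reference in 7.1 that names the section governing IMP when pregnancy is identified, separate from the existing reference for contraception and data collection.

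The sponsor and medical monitor decide the clinical content of the rule and how the text is arranged to express it.

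The cost is a few lines at the next amendment, with no change to the design, the sample size or the analysis. If subjects are still being dosed under the conflicting wording, a short clarification to sites would serve until then. If dosing has ended, the correction matters mainly for reuse of this text in later protocols.
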